Title: PHASE II RANDOMIZED PLACEBO-CONTROLLED CLINICAL TRIAL OF GENISTEIN IN REDUCING THE TOXICITY AND IMPROVING THE EFFICACY OF INTRAVESICAL THERAPY

Study Principal Investigator: [name] MD

Study Sponsor: [name]

Study Co-Principal Investigator: [name] PhD

Study Supporter: DSM Nutritional Products

Version Date: 16 Jul 2019

Schema:

E n r o ll m e n t	44 TaT1 Tis superficial bladder cancer patients scheduled to receive BCG intravesical therapy will be consented Estimated Timeline: until 44 subjects are enrolled (approximately 2 years)	R a n d o m iz a ti o n	Arm 1: BCG intravesical therapy with placebo pills for 10 weeks (22 subjects) Arm 2: BCG intravesical therapy with 30 mg genistein supplement PO TID for 10 weeks (22 subjects)	F o ll o w - u p	Arm 1: Followed-up according to standard after-treatment care: one-month post-treatment appointment and subsequent doctor visits. Arm 2: Followed-up according to standard after-treatment care: one-month post-treatment appointment and subsequent doctor visits.
--	---	---	--	---------------------------------------	--

Patients will take either 30 mg tablets of placebo or genistein supplement PO TID, for 6 weeks during BCG intravesical therapy and will continue for 4 weeks following therapy.

1. Abstract:

Patients who are treated with BCG intravesical therapy for TaT1 Tis superficial bladder cancer often develop adverse effects (urinary tract symptoms) which limit the dose (and therefore the efficacy) of therapy and result in poor quality of life. Genistein is a nutritional supplement with anti-inflammatory properties which might help alleviate adverse effects of intravesical therapy that are due to inflammation. Additionally, genistein also has anti-tumor and immunopotentiating properties and has been shown to have no known side effects. Our hypothesis is that genistein given together with BCG intravesical therapy will reduce its adverse effects and improve the efficacy of therapy. Patients (N=44) scheduled for intravesical therapy will be randomly assigned to take 30 mg tablets of genistein supplement (N=22) or placebo (N=22) PO TID during therapy and one month post therapy.

2. Introduction and Background:

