***Birth Control is not required for this study!

Exclusion Criteria:

1. Patients who are pregnant
2. Diagnosis of muscle-invasive bladder cancer
3. Unwillingness to follow study protocol and compliance procedures
4. HIV positive or immunocompromised
5. Receiving concurrent immunotherapy or chemotherapy
6. Presence of concurrent second cancer (active, not history)

7. Quality of Life:

This study follows standard of care for all superficial bladder cancer subjects. All subjects will receive standard BCG intravesical therapy for six weeks and return for a one-month post-operative visit and biopsy. Both the control and intervention arms will receive the same care, other than taking the genistein supplement or placebo. While genistein supplement is not a standard part of treatment, it has been shown to not have any significant toxicities. It is expected that the subjects taking genistein supplement will have a better quality of life due to a possible reduction in urinary symptoms, such as hematuria, infection, frequency, urgency, and retention, when compared to those subjects receiving standard treatment without the genistein supplement. Each patient's perception of quality of life will be seen indirectly throughout the BCG treatment, as it is a supplemental question on the IPSS Questionnaire.

Quality of life will be assessed for both arms during an interim analysis and stopping criteria will be determined on the degree of individual AEs as well as an interim analysis of both arms. Subjects with toxicities of Grade 3 or higher according the NCI CTCAE Version 4.0 will be immediately discontinued from the study pill. Additionally, the interim analysis will take place after 22 patients (11 on each arm) have been enrolled, treated, and biopsied. If the genistein supplement arm has statistically significant toxicities reported or greater degree of bladder cancer biopsies then we will immediately discontinue any future study enrollment. If the genistein supplement arm has significant Grade 3 toxicities, we will reduce the genistein supplement given by 1 tablet for 10 more patients, and if the toxicities persist after that, the study will be stopped.

8. Statistical Consideration:

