8.1 Power analysis

We hypothesize that, at 6 weeks, the symptom score will increase by 6 (SD = 3.5) relative to the baseline in the placebo arm, while it will only increase by 3 (SD = 3.5) in the synthetic genistein supplement arm. A sample size of 20 patients in each arm can reach 83% power to detect the hypothesized difference at the significance level of 0.05 by one-sided Mann-Whitney test.

In an effort to reach a sample size of 20 patients on each arm, we also hypothesize that there will be a 10% drop-out or non-compliance rate. We will accrue 44 patients, 22 subjects on each arm, for this study with the expectation that 10% will drop out. With a 10% drop out rate included, this would result in a total of 40 compliant patients.

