8.2.2 Secondary analysis

- a) For the secondary end point of recurrence rate defined by 10-week biopsy, the Chi-squares test is used to test the rate difference between the two arms, and a logistic regression is needed to further adjust potential covariates, e.g. total BCG therapy dose.
- b) For the secondary end point of the total dose of intravesical therapy administered over 6 weeks, we consider the two-sample t test and/or sum rank test to test the difference between two arms. If genistein supplement works by reducing symptoms and maintaining the therapy dose, we expect to see a higher total therapy dose in its arm than in the placebo arm.
- c) We will also explore the change of IPSS score over time by the GEE model in which the repeated measurements of IPSS score are treated as outcome. Treatment, time, interaction between treatment and time, and intravesical therapy dose enter the model as predictors and time-dependent covariate.

9. Adverse Event Reporting:

According to 21 CFR 312.32, *Adverse event* means any untoward medical occurrence associated with the use of a drug in humans, whether or not considered drug related. A *Serious adverse event* or *serious suspected adverse reaction* is an adverse event or suspected adverse reaction is considered "serious" if, in the view of either the

investigator or sponsor, it results in any of the following outcomes: Death, a life-threatening adverse event, inpatient hospitalization or prolongation of existing hospitalization, a persistent or significant incapacity or substantial disruption of the ability to conduct normal life functions, or a congenital anomaly/birth defect. Important medical events that may not result in death, be life-threatening, or require hospitalization may be considered serious when, based upon appropriate medical judgment, they may jeopardize the patient or subject and may require medical or surgical intervention to prevent one of the outcomes listed in this definition. Examples of such medical events include allergic bronchospasm requiring intensive treatment in an emergency room or at home, blood dyscrasias or convulsions that do not result in inpatient hospitalization, or the development of drug dependency or drug abuse.

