Adverse events will be recorded at each study visit via direct patient communication as well as through patient questionnaires. The severity of the AEs will be graded according to NCI CTCAE Version 4.0. Subjects with toxicities of Grade 3 or higher will be immediately discontinued from the study pill for the remainder of treatment. Any BCG intravesical therapy modifications will be done according to doctor analysis with an effort on alleviating toxicities as needed. In order to be evaluable, patients will need to receive at least three BCG instillations. If BCG treatment is interrupted or discontinued, only IPSS scores will be obtained via phone call. If a SAE occurs, we will promptly report it to our IRB upon discovery and follow the subject until the SAE is resolved. Adverse events will be reported to the IRB according to their requirements.

IND safety reports will be sent to the FDA in accordance with 312.32 the FDA's *Guidance for Industry and Investigators: Safety Reporting Requirements for INDs and BA/BE studies*. IND safety reports will document any aggregate adverse events, adverse reactions suspected adverse reactions, or serious adverse events. If the event is considered to be unexpected fatal or life-threatening, the IND safety report will be sent as soon as possible and within 7 business days of the investigator being notified. If necessary, the investigator will report any serious or life-threatening event initially by facsimile or telephone prior to formal submission. IND safety reports will also be submitted to the FDA if any related safety information is released from other sources. Any nonserious adverse events will be reported to the FDA in aggregate on an annual basis.

10. Data and Safety Monitoring Plan (DSMP):

Once the study has reached 50% accrual, investigators will plan to initially evaluate the results. A group of physicians from the Winship Cancer Institute at Emory University will review the data and questionnaires to see how patients are reacting to the genistein supplement arm or whether there are drug compliance issues, such as failure to take the pills per protocol. If the genistein supplement arm has statistically significant toxicities reported or greater degree of bladder cancer biopsies then we will immediately

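### The interim rule halts enrolment for a 'greater degree' of positive biopsies on genistein at 11 vs 11 without a margin or test, and the visit schedule prescribes a fuller 10-week work-up on genistein than on placebo

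*Combined protocol and SAP*

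**What the plan says.** Section 7 fixes the timing: "the interim analysis will take place after 22 patients (11 on each arm) have been enrolled, treated, and biopsied". If genistein then has "statistically significant toxicities reported or greater degree of bladder cancer biopsies then we will immediately discontinue any future study enrollment". Section 10 places the look at 50% accrual, gives the review to a group of physicians, and repeats the rule: "If the genistein supplement arm has statistically significant toxicities reported or greater degree of bladder cancer biopsies then we will immediately" end further enrolment.

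Section 8 does not mention the interim look. For recurrence at the 10-week biopsy, Section 8.2.2(a) says "the Chi-squares test is used to test the rate difference between the two arms". That is the secondary analysis, with no significance level, sidedness or continuity correction and no link to Section 7. The only level and sidedness in the plan belong to the primary endpoint in Section 8.1: "at the significance level of 0.05 by one-sided Mann-Whitney test".

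The schedule table in Section 5 differs by arm at week 10. The placebo row has cystoscopy, with biopsy recommended but optional and cytology only where indicated. The genistein row lists biopsy with pathology, and cytology, without qualification. Section 7 says that care is the same in both arms apart from the study tablets.

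**The concern.** The instruction is mandatory and immediate, but the event that triggers it is undefined. The sentence allows at least three readings:

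- **Any excess.** One more positive patient on genistein is enough.
- **Significant excess.** The words about statistical significance govern biopsies as well as toxicities. A test, a level and a sidedness are then still missing.
- **Worse disease.** Degree refers to grade or extent, not to the number of positive patients.

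With 3 positive on genistein and 2 on placebo, the first reading closes the trial and the second continues it. The physicians reviewing the data have nothing in the plan to tell them which applies.

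Two things are at stake. The trial could end on chance in a setting where the sponsor expects benefit; the abstract hypothesises that genistein "will reduce its adverse effects and improve the efficacy of therapy". And if the schedule is followed as printed, the arm that is examined more fully will tend to show more cancer, and the stopping rule acts only against that arm.

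**Working it through.** **Plan's own figure.** The plan gives no operating characteristics for the interim rule. Its one checkable figure is Section 8.1: "A sample size of 20 patients in each arm can reach 83% power to detect the hypothesized difference". With a difference of 3, SD 3.5 and Mann-Whitney efficiency 3/π, z = √(20 × 0.955 / 2) × 3/3.5 − 1.645 = 1.00, so power is 84%. A noncentral-t version gives 83.0%, so the stated figure reproduces.

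**Inputs for the interim rule.**

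- 11 per arm at the look (Section 7); 1:1 allocation (Section 5).
- The 10-week positive rate is not in the documents. Section 2 gives only recurrence within 5 years (50-80%). I assume 10-50%.

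**Model.** X (placebo) and Y (genistein) are independent Binomial(11, p) counts. All probabilities below are exact sums over the 12 × 12 possible outcomes.

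**Any excess, no true difference.** By symmetry, P(Y > X) = [1 − P(X = Y)] / 2.

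- p = 10%: (1 − 0.296) / 2 = 35.2%
- p = 20%: (1 − 0.213) / 2 = 39.3%
- p = 30%: (1 − 0.184) / 2 = 40.8%
- p = 50%: (1 − 0.168) / 2 = 41.6%

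The result is not sensitive within this range. It falls to 28% at p = 5% and 16% at p = 2%. With 9-10 assessed per arm it is 33-41%.

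**Significant excess.** For the uncorrected chi-square with genistein higher, z = [(Y − X)/11] / √[p̄(1 − p̄) × 2/11], where p̄ = (X + Y)/22. Stop if z > 1.645 (one-sided 0.05) or z > 1.960 (two-sided 0.05). Example with 5 positive on genistein and 1 on placebo: p̄ = 6/22 = 0.273, and z = 0.364 / 0.190 = 1.91. The one-sided rule stops and the two-sided rule does not.

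**Results at 11 vs 11** (pairs are placebo vs genistein):

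| Rule | False stop at 10 / 20 / 30 / 50% | Stop at 10 vs 20 / 20 vs 40 / 30 vs 60% (harm) | Stop at 20 vs 10 / 30 vs 20% (benefit) |
|---|---|---|---|
| Any excess | 35.2 / 39.3 / 40.8 / 41.6% | 64 / 79 / 89% | 16 / 21% |
| At least 3 more | 3.6 / 8.9 / 12.1 / 14.3% | 19 / 45 / 65% | 1.3 / 3.6% |
| Chi-square, one-sided 0.05 | 2.9 / 4.9 / 5.5 / 6.7% | 14 / 28 / 47% | 0.8 / 1.5% |
| Chi-square, two-sided 0.05 | 0.6 / 1.7 / 2.1 / 2.6% | 5.5 / 15.5 / 30% | 0.2 / 0.5% |

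A Yates correction or Fisher's test lowers the false stop further, to 0.1-0.9% (two-sided) or 0.6-2.6% (one-sided). Over a grid of rates from 1% to 99%, the one-sided uncorrected chi-square never exceeds 6.7%.

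**Schedule.** The figures above assume that both arms are examined equally. If some placebo patients have no biopsy or cytology while all genistein patients do, the observed placebo rate falls and every stop probability rises. The documents do not say how many placebo patients would go without, so only the direction can be given.

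**The case against.** Four counter-arguments deserve weight.

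- **The 35-42% belongs to one reading.** The biopsy phrase follows the words about statistical significance in the same clause, and those words may cover both. On that reading the false stop is at most 6.7%, which is no material problem. This stands: a reader might infer that the plan contains a stopping rule with a 40% false-stop rate, and the documents do not establish that. What they establish is that the rule is undefined.
- **Physicians review the data, and a monitoring committee reviews conduct annually.** This helps, but Section 10 gives the physicians no threshold and the action is worded as automatic. Judgement cannot be relied on to repair it.
- **A harm rule may be cautious.** When the harm is cancer at biopsy, stopping readily is defensible, and any statistical threshold at 11 vs 11 gives up detection. This stands, and it is why the threshold is the sponsor's choice. A cautious rule still has to be written as one.
- **Other text calls the 10-week biopsy standard care.** Section 5 does so, and Section 7 counts patients as biopsied before the look. That makes the arm difference in the table look like a drafting slip. It does not support an inference that placebo patients were in fact examined less. The table nevertheless is what sites follow, and it conflicts with that text.

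**Conclusion.** The concern holds as an undefined criterion fed by an unequal assessment. Depending on the reading, the chance of stopping an inert genistein on biopsies runs from 0.6% to 42%, and the chance of stopping on a true doubling from 30% to 60% runs from 30% to 89%. These are different rules, and the plan does not choose between them. The reading based on grade or extent cannot be quantified from the documents.

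The figures rest on assumed 10-week positive rates of 10-50%, 11 assessed patients per arm, and the biopsy criterion alone. The toxicity criterion in the same sentence also lacks a test and would add to any stop probability.

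A reader might also infer that the interim look inflates the type I error for the IPSS endpoint. It does not: the rule acts only on apparent harm. This should be fixed, but it does not invalidate the primary analysis.

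**What to change.** 1. **Schedule table, Section 5.** Give both rows the same 10-week assessment, for example cystoscopy with biopsy recommended and cytology if indicated. This adds no procedure.
2. **Sections 7 and 10.** Define the criterion as the proportion of assessed patients with bladder cancer at 10 weeks. Replace the undefined comparison with one prespecified margin, and print its false-stop and detection rates. Two workable examples:
   - At least 3 more positive patients on genistein at 11 vs 11: false stop 4-14%; detection 65% at 30% vs 60% and 19% at 10% vs 20%.
   - One-sided uncorrected chi-square p < 0.05: false stop 2.9-6.7%; detection 47% and 14%. With 0/1/2/3/4/5/6/7/8 positive on placebo, stop at 3/5/6/7/8/9/10/11/11 or more on genistein.

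These cut-offs apply when all 11 per arm are assessed, so the text should say what applies if fewer are. The sponsor should choose the level of caution; neither example is dictated by the plan.

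The cost is wording in two sections, the week-10 cells of one table and a short cut-off list. The downside is real: an excess of one or two patients would generally no longer stop enrolment automatically, and detection at 30% vs 60% falls from 89% under the literal rule to 65% or 47%.

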8.1 Power analysis

We hypothesize that, at 6 weeks, the symptom score will increase by 6 (SD = 3.5) relative to the baseline in the placebo arm, while it will only increase by 3 (SD = 3.5) in the synthetic genistein supplement arm. A sample size of 20 patients in each arm can reach 83% power to detect the hypothesized difference at the significance level of 0.05 by one-sided Mann-Whitney test.

In an effort to reach a sample size of 20 patients on each arm, we also hypothesize that there will be a 10% drop-out or non-compliance rate. We will accrue 44 patients, 22 subjects on each arm, for this study with the expectation that 10% will drop out. With a 10% drop out rate included, this would result in a total of 40 compliant patients.

8.2 Statistical analysis plan

8.2.1 Primary analysis

The IPSS score change at 6-week from baseline will be calculated with 95% confidence interval and compared between two experiment groups through Mann-Whitney test. The baseline, minimum three treatment period IPSS scores, and the 10-week biopsy IPSS scores are required in order for the patient to be evaluable.

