4.1 Primary objective

The primary study endpoint is the change in severity of urinary symptoms over time as determined by the IPSS questionnaire score, specifically comparing the symptoms at the 1st BCG treatment (baseline) to the symptoms at the 6th week of treatment. The difference in the degree of urinary symptoms between the placebo and genistein supplement arms will help reflect whether genistein supplement can improve the quality of life in BCG intravesical therapy patients.

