4.2 Secondary objective

- a) A secondary study endpoint will be the presence of cancer and the rate of recurrence as determined by the 10-week biopsy or subsequent standard follow-up visits.
- b) A second secondary study endpoint will be the total dose of intravesical therapy administered over the 6 weeks of treatment. If subjects develop fewer urinary tract symptoms as a result of the genistein supplement, then hypothetically, intravesical therapy dosing would not have to be reduced as much. This will be measured by looking at the level of dose reduction for each treatment week and comparing it across the two arms.

5. Study Design and Methods:

At the pre-operative office visit before intravesical therapy, eligible patients will be screened and enrolled into the study by going through the consent process and signing the consent and HIPAA forms. Each patient will need to report all other medications so that the study team can assess whether certain medications might affect trial outcome.

Patients will be randomized into Arm 1 (placebo) or Arm 2 (genistein supplement) at a ratio of 1:1 stratified by one dichotomized prognostic factor, age. The dichotomization will take place based on whether they are age 60 and above or whether they are age 59 and below. This will allow for similar age groups to be placed in each arm, so that the degree of urinary symptoms while receiving treatment is not skewed depending on the patient's age.

Patients are treated with intravesical therapy once a week for 6 weeks and then return to the office approximately four weeks later for a post-operative visit and biopsy, as is standard care. Study subjects will take their genistein or placebo tablets for a total of 10 weeks, which includes the length of their treatment, as well as the 4 weeks before the post-op visit. Each patient will fill out an International Prostate Symptom Score (IPSS) questionnaire at their baseline office visit when consented. Patients will fill out an IPSS questionnaire at each subsequent intravesical therapy session and their final one-month follow-up appointment (at 10 weeks) either in person or via phone call with a study team member. The IPSS questionnaire will gauge their urinary symptoms throughout their therapy and provide measurable symptom scores for the two arms. The biopsy at 10 weeks, as well as standard 3 months follow-up appointments, is standard care for superficial bladder patients and will help determine cancer rate of recurrence.

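### The primary Mann-Whitney test is sound, but it leaves out the age stratum used in randomisation and uses baseline IPSS only by subtraction: a small, cheap improvement, low priority

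*Combined protocol and SAP*

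**What the plan says.** Section 8.2.1 sets out the main comparison as follows: "The IPSS score change at 6-week from baseline will be calculated with 95% confidence interval and compared between two experiment groups through Mann-Whitney test". It names no covariate and no stratum, and does not say whether the test is one-sided. On evaluability it adds: "The baseline, minimum three treatment period IPSS scores, and the 10-week biopsy IPSS scores are required". A baseline score is therefore held for every analysed patient.

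Section 8.1 assumes a rise of 6 on placebo and 3 on genistein, SD 3.5 in each arm, and a one-sided Mann-Whitney test at 0.05: "A sample size of 20 patients in each arm can reach 83% power to detect the hypothesized difference".

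Section 5 randomises "at a ratio of 1:1 stratified by one dichotomized prognostic factor, age", with groups of 60 and above and 59 and below. The reason given is "so that the degree of urinary symptoms while receiving treatment is not skewed depending on the" age of the patient.

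Section 8.2.2 does plan adjustment for secondary and exploratory analyses. For recurrence, "a logistic regression is needed to further adjust potential covariates, e.g. total BCG therapy dose". For repeated IPSS scores by GEE, "Treatment, time, interaction between treatment and time, and intravesical therapy dose enter the model as predictors and time-dependent covariate". Age is named in neither.

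Section 4.1 defines the primary comparison as "specifically comparing the symptoms at the 1st BCG treatment (baseline) to the symptoms at the 6th week of treatment", while Section 5 also collects a baseline questionnaire at the consent visit.

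**The concern.** The design treats age as prognostic for the symptoms that form the primary outcome, and the analysis then drops it. Stratified allocation keeps age from adding chance imbalance between arms, but an unstratified test still counts age-related spread as noise. If age moves the change score, the test becomes conservative and gives up power.

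Baseline IPSS raises a similar question. Subtracting it is fully efficient only when the slope of week-6 on baseline IPSS is close to 1. At a lower slope, regression on baseline leaves less residual variance than subtraction does.

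With 20 analysed patients per arm and a planned type II risk of about 17%, a few points of power that need no extra patients deserve a sentence in the plan.

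**Working it through.** **Inputs from the documents.** Difference 6 − 3 = 3; change SD 3.5; 20 per arm; one-sided 0.05 (Section 8.1). The age cut is in Section 5.

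**Inputs not in the documents, so assumed.** IPSS SD at each visit (6 to 8), the baseline/week-6 correlation, the size of any age effect, and the share aged 60 or over (70% unless stated).

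**1. The plan's own figure.** Standardised difference 3/3.5 = 0.857. The Mann-Whitney efficiency under normality is 3/π = 0.955, so the effective n is 20 × 0.955 = 19.1 per arm. The noncentrality is 0.857 × √(19.1/2) = 2.65, which gives 83.0% power (noncentral t, one-sided 0.05). Simulation gives 82.3% with continuous scores and 82.4% with rounded scores. The stated 83% reproduces. The same test run two-sided has about 72–73%, so the figure holds only for the one-sided test.

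**2. Age stratum.** Suppose age shifts the change score by d, a fraction p of patients are aged 60 or over, and the total change variance stays at 3.5² = 12.25. The between-stratum variance is d²p(1 − p). Stratified allocation removes it from the true variability of the arm difference, but the unstratified test still charges for it. The effective one-sided critical value is about 1.645/√(1 − d²p(1 − p)/12.25).

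- d = 3, p = 0.7: 9 × 0.21 = 1.89; 1.89/12.25 = 0.154; 1.645/√0.846 = 1.79; type I error about 3.7%.
- d = 1, p = 0.7: 0.21/12.25 = 0.017; 1.645/√0.983 = 1.66; about 4.9%, which is negligible conservatism.

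Simulation agrees. At d = 3 and equal IPSS SDs of 7:

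| Aged 60 or over | Planned test: type I error / power | Van Elteren on change: power | Mann-Whitney on adjusted residuals: power |
|---|---|---|---|
| 50% | 3.2% / 84% | 89% | 90% |
| 70% | 3.7% / 84% | 87% | 89% |
| 85% | 4.0% / 84% | 85% | 87% |

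The two stratum-using tests hold type I error at 4.9–5.3% and 5.0–5.1%. A separate run at 70% gave 3.6% type I error for the planned test and powers of 84%, 87% and 89%. The forgone power there is 87 − 84 = 3 to 89 − 84 = 5 points.

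With a 1-point effect the planned test has 82–83% power and the residual test 84–85%. If age shifts symptom level by 3 points but not the change, the planned test is unaffected (82% power, 4.8% type I error). With no age effect, either adjusted test costs under about 1 point.

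**3. Baseline adjustment.** With baseline SD s₀ and week-6 SD s₁, a change SD of 3.5 fixes the slope at (s₀² + s₁² − 12.25)/(2s₀²). The residual variance after regression is 12.25 − (1 − slope)² × s₀². The last column is the simulated power of the residual test minus that of the planned test (normal scores, age unrelated to symptoms).

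| s₀ → s₁ | Slope | Residual variance / 12.25 | Gain (points) |
|---|---|---|---|
| 6 → 6 | 0.83 | 0.915 | +2.0 |
| 7 → 7 | 0.875 | 0.938 | +1.6 |
| 8 → 8 | 0.904 | 0.952 | +0.8 |
| 6 → 6.5 | 0.917 | 0.980 | +0.1 |
| 7 → 7.5 | 0.949 | 0.990 | −0.4 |
| 8 → 8.5 | 0.969 | 0.995 | −0.5 |
| 6 → 7 | 1.01 | 1.000 | −0.3 |
| 7 → 8 | 1.03 | 0.997 | −0.3 |
| 8 → 9 | 1.04 | 0.993 | −0.3 |

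At equal SDs the saving is worth 20/0.915 = 21.9 down to 20/0.952 = 21.0 patients per arm instead of 20. A separate run put the unequal-SD cases between +0.2 and −0.7. These used 6,000 to 20,000 replicates, so a single power near 82% carries a simulation error of about 0.3 to 0.5 points; differences of a few tenths are near noise.

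With skewed whole-number scores (assumed gamma), the planned test has 89–90% power and the residual test 91–92% at equal SDs. At slope 1 the planned test has 91% and the residual test 89–90%, a loss of 1.3–1.7 points.

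**The case against.** The strongest reply is that the planned test delivers what Section 8.1 promises. In the settings examined its one-sided power is about 82% or more, and its type I error is not inflated. A reader might infer from the missing stratum that the primary test is wrong, anti-conservative or underpowered. The documents do not support that: any distortion is in the conservative direction, and marked conservatism needs an age effect on change as large as the treatment effect itself. Section 5 speaks of the degree of symptoms, and an effect on level alone leaves the change score untouched. This part of the objection stands and limits the point to efficiency.

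The second reply also stands. A reader might infer that baseline adjustment is a sure gain of 1 to 3 points, or about 11 if the correlation were as low as 0.3. Those figures require equal IPSS SDs at both visits. The plan expects scores to rise by 3 to 6 points on treatment, so a somewhat wider week-6 spread is plausible, and half a point of extra SD removes the gain. Even its sign cannot be settled from the documents.

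A third tempting step is to make ANCOVA the primary test. Under normality about 2 points of its apparent advantage come from leaving the rank test, not from adjustment. With skewed scores at slope 1 it has about 83% power against 91% for the plan.

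What does not fall is the age stratum. Using it follows the design, costs under about 1 point if age is irrelevant, and restores the 5% level if age matters for change. The unclear baseline affects the planned change score just as much, so it needs settling whichever test is chosen.

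**Conclusion.** The point holds as a cheap improvement of low priority, not as an error. The age stratum is the firmer half: about 3 to 5 points of power at an assumed 3-point age effect on change (70% aged 60 or over, equal IPSS SDs of 7), against a cost of under about 1 point if age affects only level or nothing. Of those 5 points, about 2 (89 − 87) separate the residual test from van Elteren, which does not regress on baseline, so they depend on the equal-SD assumption.

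Baseline adjustment is worth about 1 to 2 points at equal SDs of 6 to 8. It is worth about zero, down to −0.7 with normal scores, when the week-6 SD is 0.5 to 1 point larger, and down to −1.7 with skewed scores at slope 1.

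The documents give only the change SD of 3.5; every other input is assumed. Validity here means type I error among analysed patients. The evaluability rule depends on scores collected after randomisation and is a separate matter.

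**What to change.** In Section 8.2.1:

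- Pre-specify one rank-based primary test that uses the age stratum (60 and above, 59 and below). Either choice serves: the van Elteren test on IPSS change, or the Mann-Whitney test on residuals from a regression of week-6 IPSS on baseline IPSS and age stratum, fitted to both arms pooled with arm left out.
- Keep the unadjusted Mann-Whitney test as a sensitivity analysis.
- Report a baseline- and age-adjusted between-arm difference with its interval as a supporting estimate only, since a parametric interval can disagree with a rank test.
- State that the test is one-sided at 0.05, as in Section 8.1.

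Name one baseline score and use it in Sections 4.1, 5 and 8.2.1.

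Make the change before between-arm data are reviewed. Section 7 plans an interim analysis after 22 patients, and the Section 10 review at 50% accrual includes the questionnaires. The stated stopping triggers are toxicity and biopsy results, and the documents do not say whether the look has taken place.

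The cost is a few wording edits and slightly more analysis work, with no new data, visits or patients. The downside is a possible loss of about 0.5 to 1.5 points of power if the slope of week-6 on baseline is near 1 and age has no effect.
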